6.0 LABORATORY METHODS

6.1 Specimen Preparation

Bovine teeth will be used as the hard tissue test substrate for the preparation of the 4 mm round specimens in the modified *in situ* caries model. Upon receipt at OHRI, the teeth will be sorted, cleaned and stored in 0.1% thymol solution during sample preparation procedures.

[figure not shown]
Teeth will be selected based on the following criteria:

- Have no discoloration and no markings, such as cracks, when viewed under a microscope at 20× magnification.
- Sufficient tooth surface to provide a large size specimen to meet study requirements.

Approximately two specimens will be obtained from the buccal surface of each bovine tooth. A core of enamel 4 mm in diameter will be prepared from each bovine tooth by cutting perpendicularly to the buccal surface with a hollow-core diamond drill bit.

The specimens will be ground and polished to create planar parallel dentin and enamel surfaces. All grinding/polishing will be done on a polishing surface moistened with deionized water (dw). The dentin side will be ground flat using 500 grit silicon carbide paper, followed by grinding and polishing of the enamel side. A small orientation cut will be placed on each block (see Figure 2). The enamel surface of each specimen will be ground using 1200 grit silicon carbide paper followed by 2400 and then 4000 grit silicon carbide paper. After the grinding procedures are completed, the enamel specimens will be sonicated in deionized water (dw) for two minutes and then placed under running dw for three minutes. The polishing step will involve the use of a 1 micrometer (μ m) diamond suspension on a polishing cloth. The enamel specimens will then be rinsed under a steady stream of dw, sonicated for two minutes in 2% microliquid soap and then rinsed again with dw for three minutes. Resulting specimens will have a thickness range of 1.8 to 2.2 mm. The specimen will have a minimum polished surface of 3 mm × 3 mm in the center of the enamel surface.

Figure 2
4 mm Round Bovine Enamel Specimen

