6.3 Lesion Quality

Lesions will be inclined towards an overhead light until a reflection is obtained. Acceptable lesions with an intact surface-zone will have a continuous, uniform shiny surface, with no matt areas. Lesions with matt area(s) will be rejected. The following criteria will be used to select specimens for inclusion in the study:

- The lesioned areas of each specimen should be of equal and uniform opacity; and
- The lesioned areas of each specimen should possess a surface shine when exposed to light, thereby indicating an intact surface.

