6.4 Efficacy Measurements and Evaluations

6.4.1 Surface Microhardness

The SMH test will be used to assess changes in the mineral status of partially demineralized enamel specimens. SMH will be measured using a Wilson 2100 Hardness Tester. Each enamel specimen will be secured on a 1-inch square acrylic block with sticky wax and then placed on the microhardness tester. Five baseline indentations spaced 100 μ m apart will be placed with a Knoop diamond under a 50 gram load in the center of a flattened, polished sound enamel specimen. SMH will be determined by measuring the length of the indentations using Wilson 2100 - Clemex CMT Software (version 6.0.011). For enamel specimens to be acceptable for use in the study, the mean of the five baseline indentation length must be 43 ± 3 μ m with a standard deviation of \leq 3 μ m.

After in vitro demineralization, the enamel specimens will be again SMH tested by placing five indentations 100 μ m to the left of the baseline indentations (see Figure 2). To qualify for the study, the mean (n = 5) indentation lengths of the partially demineralized specimens must be 120 \pm 20 μ m with a standard deviation of \leq 10 μ m. After 14 days of intra-oral exposure the enamel specimens will be again SMH-tested by placing five indentations 100 μ m to the right of the baseline indentations (see Figure 2). The extent of remineralization will be calculated based on the method of [Gelhard et al., 1979].

 $%SMH recovery = (D1-R)/(D1-B) \times 100$

B = indentation length (μm) of sound enamel specimen at baseline

D1 = indentation length (μ m) after in vitro demineralization

R = indentation length (μ m) after intra-oral exposure.

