7.2 Sample Size Justification

Based on previous studies we estimate the standard deviation of the differences between treatments in the crossover model to be 20 for % SMH recovery. With a sample size of 58 subjects completing the study, the study will have 80% power to detect a difference between any two treatments of 7.5 for % SMH recovery, assuming two-sided tests each conducted at a 5% significance level. Due to expected dropouts during the crossover study, the study will enroll 65 subjects.

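### Qualified enamel specimens are not balanced or randomised across a subject's three periods: a cheap gain in precision is missed, though the stated power stands

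*Combined protocol and SAP*

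**What the plan says.** **Supply of specimens.** Section 6.1: "Approximately two specimens will be obtained from the buccal surface of each bovine tooth". Under section 2, two specimens are worn in each of three periods, so a completing subject uses six.

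**Selection.** Section 6.3 introduces a visual screen with "The following criteria will be used to select specimens for inclusion in the study"; its criteria are uniform opacity and an intact, shiny surface. Section 6.4.1 requires the sound-enamel mean (B) to be 43 ± 3 µm. After demineralisation, the mean "indentation lengths of the partially demineralized specimens must be 120" ± 20 µm. The within-specimen SD may be at most 3 µm for B and 10 µm for D1. Both readings precede placement in the mouth.

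**Endpoint.** With R the length after wear, % SMH recovery is 100 × (D1 − R)/(D1 − B). The two specimens are averaged by subject and treatment (section 7.1).

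**Allocation and model.** Section 4.3 randomises treatment order only. Sections 5.2, 5.8 and 6 describe placing and preparing specimens without saying which goes to which subject or period. The ANOVA in section 7.1 has subject, period and product, with no term for D1 or source tooth.

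**Power.** Section 7.2, citing earlier studies: "we estimate the standard deviation of the differences between treatments in the crossover model to be 20 for % SMH recovery". On that basis it claims 80% power against a 7.5-point gap between any pair of products when 58 subjects finish.

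**The concern.** The crossover gains its efficiency from within-subject differences. If the lesions a subject wears in one period are softer or harder at the start than those worn in another, the difference may carry specimen variation unrelated to product. The acceptance limits restrict each specimen separately; they do not make a subject's periods alike.

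Two cores from one tooth may also share a subject-period. Averaging them then does little to reduce tooth-to-tooth variation, and that variation falls on a single product for that subject.

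The secondary measures are more exposed in one respect. Microradiography (section 6.4.5) is done on sections cut after the hardness work, and fluoride uptake (section 6.4.2) is an amount per unit area. Neither has a pre-treatment value or any scaling by the starting lesion. What is at stake is precision that could be recovered from readings already taken.

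**Working it through.** **1. The plan's own figure.** Inputs from section 7.2: SD of differences 20, difference 7.5, 58 completers, two-sided 5%. For a paired t-test with 57 degrees of freedom, the noncentrality is 7.5 × √58 / 20 = 2.86 and power is 80.2%. At 57 completers it is 79.5%, so 58 is the smallest number that reaches 80%. The stated figure reproduces.

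**2. Range of starting lesions.** From section 6.4.1, D1 runs from 100 to 140 and B from 40 to 46. So D1 − B runs from 100 − 46 = 54 to 140 − 40 = 100 µm, a ratio of 1.85.

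**3. How D1 reaches the endpoint.** Hold B at 43 and let x = D1 − 43, so x runs from 57 to 97. The score is 100 × gain/x. If specimens are drawn independently and two are averaged per period, the variance of a period difference due to D1 is 2 × (V/2) = V, the variance of one specimen's score.

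The documents give limits for D1 but no distribution. If D1 is assumed uniform over the whole window:

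- mean of 1/x = ln(97/57)/40 = 0.01329
- mean of 1/x² = 1/(57 × 97) = 0.0001809
- SD of 1/x = 0.00205

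The D1 contribution is then:

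- gain proportional to x: the score is constant, so SD 0
- fixed gain g: SD = 100 × g × 0.00205
- 25 µm gain at the centre of the window, half fixed and half proportional: SD = 100 × 12.5 × 0.00205
- constant final R: score = 100 − 100(R − 43)/x, so SD = 100 × (R − 43) × 0.00205

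If instead D1 has an SD of 5 to 8 µm around 120, then to first order a fixed gain gives SD = 100 × g × SD(D1)/77².

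**4. Effect on power.** Subtract the contribution from the planning variance of 400 and recompute at n = 58, starting from 80.2%.

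| Assumption | SD from D1 | Share of 400 | Power if all removed |
|---|---|---|---|
| Proportional gain | 0 | 0% | 80.2% |
| Half fixed, half proportional, 25 µm, uniform D1 | 2.6 | 1.6% | 80.8% |
| Fixed 20 µm, D1 SD 5 | 1.7 | 0.7% | 80.5% |
| Fixed 30 µm, D1 SD 8 | 4.0 | 4.1% | 81.8% |
| Fixed 20 µm, uniform D1 | 4.1 | 4.2% | 81.8% |
| Fixed 30 µm, uniform D1 | 6.1 | 9.5% | 83.9% |
| Constant R = 85, uniform D1 | 8.6 | 18.5% | 87.5% |
| Constant R = 95, uniform D1 | 10.7 | 28.4% | 91.3% |

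These are ceilings, because they suppose that all variation due to D1 is removed. D1 is itself a mean of five indentations with SD up to 10, so its standard error can reach 10/√5 = 4.5 µm. Matching on it is therefore imperfect.

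**5. Cores from one tooth.** If two cores with correlation ρ share a subject-period, the variance of their mean is (σ²/2)(1 + ρ). For an assumed ρ of 0.2 to 0.6, the specimen part of the variance rises by 20% to 60%. The documents do not give the size of that part, so no power figure follows.

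**The case against.** The endpoint already divides by each specimen's own D1 − B, lesions pass a numerical window and a visual screen, and two specimens are averaged. All of this stands. It is why the lower end of the range is zero, and why the lesions cannot be called uncontrolled.

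A reader might infer four stronger things that the documents do not support.

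- **That the trial is underpowered.** The SD of 20 comes from previous studies and may already include specimen variation; the documents do not say. The subtraction above assumes that it does.
- **That a product is favoured.** Treatment order is randomised and period is a fixed effect. A drift in lesion severity from batch to batch is therefore absorbed by period. Nothing suggests that placement depends on product: the study dentist and laboratory technicians are blinded (section 4.4), although the plan does not say who picks the specimens.
- **That the effect exceeds the target difference.** With B = 43, a 20 µm gain scores 20/57 = 35.1% at D1 = 100 and 20/97 = 20.6% at D1 = 140. That 14.5-point gap compares two single specimens at opposite edges of the window. The 7.5 points are a mean difference over 58 subjects, so the two are not comparable.
- **That power could reach 87% to 91%.** This needs every specimen to finish at the same hardness and D1 to fill the window evenly. At R = 95, recovery would run from 5/57 = 9% to 45/97 = 46% according to D1 alone. Nothing in the plan supports that.

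The placing of two cores from one tooth together is likewise a possibility that the plan leaves open, not something it prescribes. What survives the objection is that no allocation rule is given and that scaling cancels starting severity only under proportional rehardening, which the plan does not claim.

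**Conclusion.** This is a worthwhile, low-cost improvement in precision. It is not an error in the sample size and not a source of bias. The plan leaves D1 free to differ across a subject's periods anywhere from 100 to 140 µm and lets cores from one tooth share a period.

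For % SMH recovery the possible gain is zero under proportional rehardening and about 0.3 to 4 power points under a fixed gain of 20 to 30 µm. It is larger only if final hardness is constant whatever the start. These figures rest on assumed recovery patterns and D1 distributions, with B held at 43. The planned 80% power stands. Microradiography and fluoride uptake may gain as well, but the documents do not allow that gain to be sized.

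**What to change.** Add an allocation rule to section 6, with a cross-reference in section 4.3:

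- Within each preparation batch, rank qualified specimens on D1 and form sets of six with similar D1.
- Assign one set to each subject and allocate two specimens to each period at random, from a list prepared by the statistician.
- Avoid placing two cores from the same tooth in the same subject-period.
- Record D1 and a tooth identifier on the specimen tracking sheet.

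The cost is a sorting and allocation list built on readings already taken; no extra specimens, visits or assays are needed. Specimens must be pooled and sorted by batch before use, not taken as they are prepared. Working by batch avoids holding all 65 × 6 = 390 in storage at once. Matching on a five-indentation mean will not remove all starting-lesion variation. If pooling proves impractical, a pre-specified covariate for the mean D1 of the two specimens would recover part of the gain, but it would not separate cores from the same tooth.

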6.2 Lesion Creation

The enamel specimens will be partially demineralized using a modification of the method described by White [1987]. The 4 mm round bovine specimens will be immersed for 16 hours at 37° C under static conditions in 40 ml of an acid buffer (0.05 mol/L lactate), 50% saturated with respect to hydroxyapatite and with 0.2% (wt/vol) carbopol 907 (BF Goodrich Co., USA) added (pH adjusted to 5.0 using KOH), and then rinsed thoroughly with deionized water. The demineralized enamel specimens will then be stored in a moist environment to prevent dehydration.

6.3 Lesion Quality

Lesions will be inclined towards an overhead light until a reflection is obtained. Acceptable lesions with an intact surface-zone will have a continuous, uniform shiny surface, with no matt areas. Lesions with matt area(s) will be rejected. The following criteria will be used to select specimens for inclusion in the study:

- The lesioned areas of each specimen should be of equal and uniform opacity; and
- The lesioned areas of each specimen should possess a surface shine when exposed to light, thereby indicating an intact surface.

6.4 Efficacy Measurements and Evaluations

6.4.1 Surface Microhardness

The SMH test will be used to assess changes in the mineral status of partially demineralized enamel specimens. SMH will be measured using a Wilson 2100 Hardness Tester. Each enamel specimen will be secured on a 1-inch square acrylic block with sticky wax and then placed on the microhardness tester. Five baseline indentations spaced 100 μ m apart will be placed with a Knoop diamond under a 50 gram load in the center of a flattened, polished sound enamel specimen. SMH will be determined by measuring the length of the indentations using Wilson 2100 - Clemex CMT Software (version 6.0.011). For enamel specimens to be acceptable for use in the study, the mean of the five baseline indentation length must be 43 ± 3 μ m with a standard deviation of \leq 3 μ m.

After in vitro demineralization, the enamel specimens will be again SMH tested by placing five indentations 100 μ m to the left of the baseline indentations (see Figure 2). To qualify for the study, the mean (n = 5) indentation lengths of the partially demineralized specimens must be 120 \pm 20 μ m with a standard deviation of \leq 10 μ m. After 14 days of intra-oral exposure the enamel specimens will be again SMH-tested by placing five indentations 100 μ m to the right of the baseline indentations (see Figure 2). The extent of remineralization will be calculated based on the method of [Gelhard et al., 1979].

 $%SMH recovery = (D1-R)/(D1-B) \times 100$

B = indentation length (μm) of sound enamel specimen at baseline

D1 = indentation length (μ m) after in vitro demineralization

R = indentation length (μ m) after intra-oral exposure.

6.4.2 Enamel Fluoride Uptake

The microdrill enamel biopsy technique as described by [Sakkab et al., 1984] will be used to analyze the fluoride content of the partially demineralized enamel specimens. Each enamel specimen will be mounted perpendicular to the long axis of a drill bit attached to a specially designed microdrill and drilled to a depth of ~100 µm through the entire lesion (four cores per specimen; see Figure 2).

The drilling and sample collection will be performed in a static-controlled atmosphere to prevent loss of enamel powder due to charging effects. The enamel powder sample, pooled from the four drilling samples, will be transferred to an analyzer cup cap. 20 microliters (μ I) of 0.5 Molar (M) Perchloric Acid (HClO₄) will be added to the enamel powder and the cap gently swirled to dissolve the powder. To the analyzer cap containing the 20 μ I of HClO₄/enamel powder, 40 μ I of citrate/ ethylene-diamine-tetraacetic acid (EDTA) buffer and 40 μ I of de-ionized water will be added and immediately analyzed for fluoride content using a fluoride specific electrode and pH/Ion meter. The diameter of the drill hole will be determined using a calibrated microscope interfaced with an image analysis system. The amount of fluoride-uptake by enamel will be calculated based on the amount of fluoride divided by the area of the enamel cores and expressed as μ g F/cm².

6.4.3 Net Acid Resistance test

To test whether the dentifrice imparts acid resistance to the enamel after 14 days of intraoral exposure, a second in vitro demineralization will be repeated following the same protocol as described above on the two enamel specimens. SMH will be then evaluated by placing 5 indentations 100µm to the right of the indentations placed *in situ* remineralization (See Figure 2). The %NAR will be calculated by the method of Corpron [Corpron et al., 1986]:

% Net Acid Resistance = [(D1-D2) / (D1-B)] * 100

B= Indentation length (µm) of sound enamel at baseline

D1= Indentation length (µm) after first in vitro demineralization

D2= Indentation length (µm) after second in vitro demineralization

Acid resistance is indicative of any protection that the treatments and intra-oral exposure may afford the enamel specimens. The net loss of enamel due to clinical caries is the result of multiple cycles of demineralization and repair (remineralization). It is well established that repaired enamel is more resistant to subsequent acid challenges.

6.4.4 Comparative Acid Resistance test

This measure takes a different approach to understanding whether the enamel formed during remineralization is more resistant to acid than the original enamel. Using the data from the two enamel specimens, the equation used will compare explicitly the reduction in SMH brought by the first and second acid challenges:

% Comparative Acid Resistance = [(D2-R) / (D1-B)] * 100

B= Indentation length (μm) of sound enamel at baseline

R= Indentation length (µm) of enamel after *in situ* remineralization

D1= Indentation length (µm) after first in vitro demineralization

D2= Indentation length (µm) after second in vitro demineralization

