2. STUDY DESIGN

This will be a double blind, single center, 3-way crossover design study. Two to three days before the start of each treatment period the subjects will have their teeth cleaned to remove all accessible plaque and calculus and will be provided with a non-fluoride dentifrice to use until their next visit. At the beginning of each testing period, two gauze-covered 4 mm round partially demineralized bovine enamel specimens will be placed in the buccal surface of two posterior denture teeth (the specimen site may extend into the buccal flange area, if needed) of the same side of the partial denture. Once specimens are placed, subjects will wear their partial dentures twenty-four hours a day and use their assigned toothpaste twice daily, as instructed, until their next visit. Specimens will be removed after two weeks, and the subjects will undergo at least a four- to five-day washout period followed by another cleaning and two to three day lead in period. This process will be repeated until all subjects have used all three test products. Changes in the mineral content of the enamel specimens will be assessed using surface microhardness (SMH) and transverse microradiography (TMR). Enamel fluoride uptake (EFU) will be determined using the microdrill enamel biopsy technique. In addition, the net acid resistance (NAR) and the comparative acid resistance (CAR) of the remineralized enamel specimens will be determined.

2.1 Study Schedule:

	Visit	Visit	Visit	Visit
	1	2, 5, 8	3, 6, 9	4, 7, 10
	Screening	Prophy	Begin Tx	End Tx
Informed Consent	X			
Medical history review	X	X	X	Х
Oral Soft Tissue exam	X	X	X	Х
Oral Hard Tissue exam	X	X (v2 only)		X (v10 only)
Salivary Flow Rate assessment	X			
Inclusion/Exclusion criteria	X			
Continuance Criteria		X	X	X
Randomization		X		
Adverse Event monitoring		X	X	X

Placement of specimens		Х	
Removal of specimens			X
Issue washout toothpaste	X		
Return washout toothpaste		Х	
Issue study products and diary		X	
Return study products and diary			X
Study close-out			X (v 10 only)

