7. STATISTICAL ANALYSES AND SAMPLE SIZE JUSTIFICATION

7.1 Statistical Analyses

The mean % SMH recovery will be calculated using the four sets of indentations within each enamel specimen. The mean fluoride uptake will be calculated using the four samples within each enamel specimen. The mean % SMH recovery, mean fluoride uptake, mean acid resistance and mean ΔZ , L, SZ_{max} will be computed for the two enamel specimens within a subject by treatment; if a subject is missing an enamel specimen, the available enamel

specimen will be used. Analyses of fluoride uptake will be performed after using a natural logarithm transformation because the measurements generally are not normally distributed.

The treatments will be compared using analysis of variance models (ANOVA) suitable for a crossover study. The models will include random effects for subject and fixed effects for study period, and product. The random effects will model the correlation and variances over time between treatments. The primary comparison of interest will be to determine if the test treatment to be statistically significant compared to the positive control treatment. Secondary comparisons will be to determine if the test treatment to be statistically significant compared to the negative control treatment and if the positive control treatment to be statistically significant compared to the negative control treatment. A 5% significance level will be used for all tests. No alpha-level adjustments for multiple comparisons adjustments will be applied.

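### Does the Comparative Acid Resistance formula in Section 6.4.4 run the wrong way for its name?

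*Combined protocol and SAP*

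**What the plan says.** Section 2 lists two acid-challenge outcomes: "the net acid resistance (NAR) and the comparative acid resistance (CAR) of the remineralized enamel specimens will be determined". Section 6.4.3 gives the first as "Net Acid Resistance = [(D1-D2) / (D1-B)] * 100" and adds: "Acid resistance is indicative of any protection that the treatments and intra-oral exposure may afford the enamel specimens". Section 6.4.4 introduces the second as a different way of "understanding whether the enamel formed during remineralization is more resistant to acid than the original enamel", says that it compares the hardness lost at the first and second challenges, and prints "Comparative Acid Resistance = [(D2-R) / (D1-B)] * 100". B, D1, R and D2 are defined there as indentation lengths on sound enamel, after the first demineralization, after the intra-oral phase and after the second demineralization. Section 6.4.1 uses the same B, D1 and R for % SMH recovery.

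Section 7.1 refers to the acid outcomes only in a list that includes "mean fluoride uptake, mean acid resistance". It does not separate the two measures or give a favourable direction for either. It also states: "No alpha-level adjustments for multiple comparisons adjustments will be applied".

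**The concern.** Two outcomes share the words acid resistance but move in opposite directions. NAR rises when the specimen is harder after the second challenge; CAR falls. A reader who takes the name at face value could report a significantly higher CAR for the test dentifrice as better resistance, when it means more softening on re-challenge.

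A second feature adds to the unease. For each specimen, CAR is exactly % SMH recovery minus % NAR. A product that remineralizes more but ends at the same D2 has the higher CAR, and CAR might be counted as separate support when it is built from the same readings as the other two. What would be at stake is the sign, and the sentence written about it, for one outcome that does not drive the sample size.

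**Working it through.** **Inputs.** B = 43 ± 3 µm and D1 = 120 ± 20 µm are the acceptance limits in Section 6.4.1. The SD of treatment differences of 20, the difference of 7.5 and the 58 completers are in Section 7.2; all concern % SMH recovery. The documents give no values for R and D2, so those below are assumptions for illustration.

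**The plan's own figure.** For a paired comparison with n = 58, the noncentrality is 7.5 / (20/√58) = 2.86. The noncentral t with 57 degrees of freedom gives 80.2% power, which agrees with the stated 80%. CAR plays no part in it.

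**Sign of the denominator.** D1 − B lies between 100 − 46 = 54 µm and 140 − 40 = 100 µm for qualifying specimens. It is always positive, so the direction of CAR is set by D2 − R alone.

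**Direction.** At the target values D1 − B = 120 − 43 = 77 µm. With R = 90 µm:

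| D2 (µm) | NAR = 100(D1 − D2)/77 | CAR = 100(D2 − R)/77 |
|---|---|---|
| 90 | 39.0% | 0% |
| 100 | 26.0% | 13.0% |
| 110 | 13.0% | 26.0% |
| 167 | −61.0% | 100% |

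So 0% means no further softening, and 100% means as much softening as the original enamel showed. Lower is more resistant.

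**Identity.** 100[(D1 − R) − (D1 − D2)]/(D1 − B) = 100(D2 − R)/(D1 − B). Hence CAR = % SMH recovery − % NAR for each specimen. It carries over to means and treatment contrasts when the same specimens supply R and D2. Section 7.1 allows a subject's value to rest on one specimen if the other is missing, so where R is available without D2 the equality of means is no longer exact.

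**Dependence on R.** Hold D2 at 110 µm, so that NAR is 13.0% throughout:

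| R (µm) | SMH recovery | D2 − R (µm) | CAR |
|---|---|---|---|
| 90 | 30/77 = 39.0% | 20 | 26.0% |
| 105 | 15/77 = 19.5% | 5 | 6.5% |

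The specimen with the higher CAR did lose more hardness at the second challenge, 20 against 5 µm. CAR reports that correctly. Its better recovery appears under SMH recovery, and the equal end state appears under NAR.

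**Effect on the tests.** A reversed scale, 100 − CAR, gives every treatment contrast the same size with the opposite sign. The standard error and the two-sided p-value stay the same.

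**The case for a change.** The strongest case for a change is that the name points one way and the number the other, that no section states the favourable direction, and that Section 7.1 does not say whether its single phrase covers NAR, CAR or both. All of that is true, and the cure would cost a few sentences.

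The case can be pressed with a probability. Suppose the test product gains the planned 7.5 points of SMH recovery with no NAR difference, and NAR differences also have an SD of 20. CAR then rises by 7.5 points. The SD of CAR differences is 20√(2(1 − ρ)), where ρ is the correlation between the SMH recovery and NAR differences: 28.3, 20.0 or 12.6 for ρ = 0, 0.5 or 0.8. With 58 completers the chance of a significantly higher CAR is 51%, 80% or 99%. These figures depend on inputs that the documents do not give. If half the gain carries into NAR they become 17%, 29% and 60%; with a NAR SD of 30 and no NAR difference they become 34%, 57% and 86%. Section 6.4.3 itself expects repaired enamel to resist later acid better, so a zero NAR gain is a doubtful default. In any case these are chances of a true difference in D2 − R being detected, not of its sign being misread.

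The absence of multiplicity adjustment adds nothing, because no adjustment would correct a sign. The identity is not a fault either: it is ordinary to combine the same readings to answer another question, and no section presents CAR as independent evidence. Whoever writes the report should still not count it as a third confirmation of benefit.

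What stands is an unhelpful label and an unstated direction.

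**Conclusion.** No change to the plan follows. The formula does what Section 6.4.4 says: it sets softening at the second challenge against softening at the first, and a value below 100% answers yes to the question of greater resistance than the original enamel. The direction follows from the printed ratio and the definitions beside it. The phrase in Section 7.1 reads naturally as covering both measures listed in Section 2 and defined in Sections 6.4.3 and 6.4.4. An analyst who follows the text would compute the right quantity and, seeing indentation lengths, would read lower as more resistant; the two companion outcomes needed to judge overall benefit are already measured.

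The cost of leaving the text alone is a possible slip in describing one outcome. The direction, the 0% and 100% reference points and the per-specimen identity are exact and need no assumption beyond longer indentations meaning softer enamel. The worked percentages use the protocol's target B and D1 with assumed R and D2. Stating the direction would move no estimate, two-sided p-value or sample size, so this is missing detail that analysts fill sensibly.
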